8.2.6 Preparation

Please refer to the Pharmacy Manual of SGI-110 (guadecitabine) for a comprehensive description of guadecitabine preparation.

OSHA Guidelines for handling cytotoxic drugs outlined in the American Journal of Hospital Pharmacy must be followed ²³. As with other potentially toxic anti-cancer agents, care should be exercised in the handling and preparation of guadecitabine. The use of gloves and protective garments is recommended. Preparation should occur in a vertical laminar flow biological hood or per institutional standards using proper aseptic technique. If guadecitabine SGI-110 contacts the skin, it should be immediately be treated with borax buffer solution pH 10 followed by washing immediately and thoroughly with soap and water. If guadecitabine contacts the mucous membranes, flush thoroughly with water.

Drug spilling can be inactivated by 2 N sodium hydroxide solution or Water and Kericide CR Biocide B which consist of a blend of stabilized chlorine dioxide and a quaternary ammonium compound.

Disinfect biological safety cabinet by wiping surfaces with 70% isopropanol or ethanol solution or by established pharmacy standards.

Note: Please follow your institutional SOPs regarding any additional requirements or processes.

Reconstituted drug product is intended for subcutaneous administration at a maximum concentration of 100 mg/mL. The required volume from the diluent vial is drawn into a syringe for reconstitution and emptied into the vial containing guadecitabine for injection.

8.2.7 Route of administration for this study

Subcutaneous. Please refer to pharmacy manual for more details on SGI-110 Administration.

8.2.8 Incompatibilities:

None known

NU Study Number: NU 16G03
Merck Study Number: 3475-244

8.2.9 Availability & Supply

Astex will supply guadecitabine directly to Northwestern University at no charge to subjects participating in this clinical trial. Investigational product resupply will need to be requested at least 2 weeks in advance. Site-specific drug order forms will be provided prior to study activation and will be used to order drug supply directly from Astex.

8.2.10 Side effects

Please see current Investigator's Brochure for a complete list of adverse events.

8.2.11 Nursing implications

Ice packs can be used for painful injection site as a comfort measure

9.0 CORRELATIVES/SPECIAL STUDIES

To test the hypothesis that the combination of guadecitabine and pembrolizumab reactivates immune responses by allowing re-expression of tumor antigens silenced epigenetically, we will measure several endpoints:

- NY-ESO-1 and MAGE antigens' promoter methylation (pyrosequencing) and mRNA expression levels (quantitative RT-PCR) will be measured before and after treatment in DNA (plasma and/or tumor biopsies) and RNA (tumor biopsies), respectively.
- Cytokine response (IFN γ , IL2, IL6, IL10, TNF α) will be measured in plasma by ELISA.
- Measure LINE 1 methylation in DNA extracted from PBMCs (Days 1 and 5 of cycles 1 and 2)
- Expression of the PD1 ligands (L1) will be measured by IHC in archival tumors.
- Tumor infiltrating lymphocytes (TILs) will be quantified in tumor biopsies before and after treatment (IHC). All biological parameters will be correlated with clinical endpoints (RR and PFS).

Please see the Laboratory Manual (LM) for specific details on correlative study procedures, handling, preserving, and shipping. The table below summarizes the tests that will be performed for correlative endpoints:

Correlative Samples summary				
Correlative study (sample type)	Archival tissue	Fresh biopsy or paracentesis or thoracentesis.	PBMC	Plasma
Mandatory or Optional	Mandatory	Mandatory except the sample collected at ≥ 6 months which is optional	Mandatory except the sample collected at ≥ 6 months which is optional	Mandatory except the sample collected at ≥ 6 months which is optional

NU Study Number: NU 16G03
Merck Study Number: 3475-244

Timing (+/- windows)	Baseline (may be procured up to 3 months from registration)	Pre-treatment C1D1 (≤ 7 days) but after registration); C2D8 (+2 days) and ONE OPTIONAL sample collection at anytime from ≥ 6 months and before the safety follow-up visit.	Pre-treatment C1D1(≤ 4 days); C1D5; Pre-treatment C2D1(≤ 4 days); C2D5; Follow up visit; and ONE OPTIONAL sample collection at anytime from ≥ 6 months and before the safety follow-up visit.	For cytokine response Pre-treatment C1D1 (≤ 4 days); C2D1 (≤ 4 days) C3D1 (≤ 4 days) and at Follow up visit. For DNA analysis C1D1(≤ 7 days); C2 D8(+2 days)-at the time of biopsy /paracentesis/ thoracentesis) and ONE OPTIONAL sample collection for both cytokine response and DNA analysis, at any time from ≥ 6 months and before the safety follow-up visit.
Volume Needed (blood only)	NA	NA	5-8ml	5-8mL
Tube type needed (blood only)	NA	NA	Sodium citrate	Sodium citrate
Tissue thickness and/or # slides (tissue only)	5-6 microns 6-10 slides	3 core biopsies for research. Tissue should be tested by pathology for tumor confirmation		NA
Processing center		IR	PCF	PCF

NU Study Number: NU 16G03
Merck Study Number: 3475-244

Sample handling/processing instructions	RT, ship as described	The first core will be snap frozen upon collection. The second core will be formalin-fixed, paraffin-embedded (FFPE). The third core will be snap frozen upon collection. Freshly collected paracentesis/thoracentesis samples will be sent immediately to the [name] lab for processing.	Separate PBMCs and plasma. Freeze PBMCs	Freeze after plasma separation
Shipping/delivery info		[name] Lab [name]	[name] Lab [name]	[name] Lab [name]
Storage needs	[name] Lab [name]	[name] Lab [name]	[name] Lab [name]	[name] Lab [name]
Analysis center	Qualtek and [name] Lab	[name] Lab	[name] Lab	[name] Lab
Assay methodology	IHC	DNA, RNA extraction	DNA extraction	DNA extraction Cytokine ELISA

The archived tumor tissue specimens may be from surgery or from a diagnostic biopsy of primary or metastatic tumor specimen, and may be procured up to 3 months from registration study. Unavailability of archived tissue will not render subject ineligible for study. Subjects will be consented to optional storage of any remaining tumor and plasma samples after protocol- specified studies are complete. Stored tumor and plasma samples will be reserved for future cancer-related research. Tumor and plasma samples for future use will be stored at Northwestern University's local laboratory:
 [name] Lab
 [name]
 [name]
 [contact]

10.0 STATISTICAL CONSIDERATIONS

Statistical analysis of this study will be the responsibility of the Biostatistics Core Facility of the Robert H. Lurie Comprehensive Cancer Center.

10.1 Study Design

This is a multi-center non-randomized, open label phase II study. Study endpoints are defined in Section 2.0. A safety run-in cohort has been designed for the first six subjects enrolled, in order to ensure the safety of this experimental combination of

NU Study Number: NU 16G03
Merck Study Number: 3475-244

guadecitabine and pembrolizumab.

10.2 Sample Size and Accrual

We will utilize the optimum two-stage design and we anticipate enrolling 35 evaluable patients. This two-stage design to test the null hypothesis that $RR \leq 0.10$ versus the alternative that $RR \geq 0.30$ (where RR is calculated via RECIST v1.1) has an expected sample size of 22.5 and a probability of early termination of 0.71 when $RR = 0.10$. If the drug combination is actually not effective, there is a 0.047 probability of concluding that it is (the target for this value was 0.050). If the drug is actually effective, there is a 0.098 probability of concluding that it is not (the target for this value was 0.100). Subjects who are not evaluable for response will be replaced so up to 46 subjects may be enrolled.

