Statistical Methodology	
This is a non-randomized, open label phase II study. Study endpoints are defined in Section 6.0
 
We will utilize the optimum two stage design, and we anticipate enrolling 35 evaluable patients. This two-stage design, which will test the null hypothesis that ORR<=0.10 versus the alternative that ORR>=0.30 (where ORR is calculated via RECIST v1.1), has an expected sample size of 22.5 and a probability of early termination of 0.71 when ORR=0.10. If the drug combination is actually not effective, there is a 0.047 probability of concluding that it is (the target for this value was 0.050). If the drug is actually effective, there is a 0.098 probability of concluding that it is not (the target for this value was 0.100). After testing the drug on 18 patients in the first stage, consideration will be given to trial termination if 2 or fewer patients demonstrate clinical benefit (CR, PR, or SD for at least 3 months). If the trial goes on to the second stage, a total of 35 evaluable patients will be studied. If the total number responding is less than or equal to 6, the combination is rejected. Subjects who are not evaluable for response will be replaced so that up to 46 subjects will be enrolled.

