10.4.2 Efficacy Criteria

As this is a two-stage design, an interim efficacy analysis is planned after 18 patients are evaluable (see 10.2 for additional details). After testing the drug on 18 patients in the first stage, consideration will be given to trial termination if 2 or fewer patients demonstrate clinical benefit (CR, PR, or SD for at least 3 months). If the trial goes on to the second stage, a total of **35 evaluable**

NU Study Number: NU 16G03

Merck Study Number: 3475-244

patients will be studied. If the total number responding is less than or equal to 6, the combination is rejected.

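### The stated early-termination probability of 0.71 should be 0.73; it contradicts the expected sample size of 22.5 given in the same sentence

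*Combined protocol and SAP*

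**What the plan says.** Section 10.2 adopts Simon's optimum two-stage design with a null response rate of 0.10 and an alternative of 0.30, response being judged by RECIST v1.1. It gives the design "an expected sample size of 22.5 and a probability of early termination of 0.71 when" the response rate is 0.10, with a type I error of 0.047 and a type II error of 0.098. The Statistical Methodology entry of the Study Summary gives the same figures: the design "has an expected sample size of 22.5 and a probability of early termination of 0.71 when ORR=0.10".

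The boundaries are in the Study Summary and section 10.4.2. The interim look comes at 18 evaluable patients, when "consideration will be given to trial termination if 2 or fewer patients demonstrate clinical benefit". If the trial continues, 35 evaluable patients are studied, and the combination is rejected if 6 or fewer respond. Section 10.4.2 contains neither the 0.71 nor the 22.5. It matters here only for the boundaries and for what the interim rule counts.

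**The concern.** Once the stage sizes are fixed, the expected sample size and the early-termination probability determine each other. The two values printed in one sentence do not agree, so at least one is wrong. Both are operating characteristics of the primary design, and a reader would expect to reproduce them exactly from the boundaries.

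At stake is the accuracy of the design description. If the stated probability were right, either the boundaries or the expected sample size would be in doubt. If it is wrong, anyone who quotes it gives an incorrect chance of stopping under the null hypothesis.

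**Working it through.** **Inputs**

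- Null rate p0 = 0.10 and alternative p1 = 0.30 (Study Summary; section 10.2).
- First stage n1 = 18, stop at r1 = 2 or fewer (Study Summary; section 10.4.2).
- Total n = 35, reject at r = 6 or fewer (Study Summary; section 10.4.2).

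The calculation takes the first-stage count to be RECIST responses, because section 10.2 states its figures for a RECIST response rate.

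**Early-termination probability (PET) at p0**

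PET = P(X ≤ 2 | 18, 0.10)

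- P(X = 0) = 0.9^18 = 0.1501
- P(X = 1) = 18 × 0.1 × 0.9^17 = 0.3002
- P(X = 2) = 153 × 0.01 × 0.9^16 = 0.2835

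The sum is 0.7338. The plan states 0.71.

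**Expected sample size at p0**

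EN = n1 + (1 − PET)(n − n1) = 18 + 0.2662 × 17 = 22.53. The plan states 22.5.

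**Error rates**

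P(declare active) = Σ over x = 3 to 18 of P(X1 = x | 18, p) × P(X2 ≥ 7 − x | 17, p)

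- At p = 0.10: 0.0474. The plan states a type I error of 0.047.
- At p = 0.30: 0.9016, so the type II error is 0.0984. The plan states 0.098.

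| Quantity | Stated | Exact | Reproduces |
|---|---|---|---|
| PET at 0.10 | 0.71 | 0.7338 | No |
| Expected N at 0.10 | 22.5 | 22.53 | Yes |
| Type I error | 0.047 | 0.0474 | Yes |
| Type II error | 0.098 | 0.0984 | Yes |

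Three of the four figures match to the last printed digit, which confirms that the design has been read correctly.

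**Can rounding explain the difference?**

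- An EN printed as 22.5 lies between 22.45 and 22.55. Then PET = 1 − (EN − 18)/17 lies between 0.732 and 0.738.
- A PET printed as 0.71 lies between 0.705 and 0.715. Then EN = 18 + 17(1 − PET) lies between 22.8 and 23.0. At exactly 0.71 it is 18 + 17 × 0.29 = 22.93.

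The ranges do not overlap, so rounding is not the cause.

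**Could 0.71 belong to another design?**

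A search over two-stage designs with total N from 20 to 45, type I error at most 0.05 and type II error at most 0.10 found 2/18, 6/35 to have the lowest EN, as the plan claims. No qualifying design has both a PET that rounds to 0.71 and an EN that rounds to 22.5. Among those whose PET rounds to 0.71, the lowest EN is 23.4, from a first stage of 19 with r1 = 2 (PET 0.705) and a total of 34. With a total of 35 that first stage gives 23.7. At n1 = 18, r1 = 1 gives a PET of 0.450 and r1 = 3 gives 0.902.

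**The case against.** The strongest objection is that nothing depends on the 0.71. The boundaries, sample size, error rates and expected sample size are right, and the trial is sized and judged on those. This stands, and it keeps the point minor.

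The second objection is that the interim rule does not count responses. Section 10.4.2 considers stopping when "consideration will be given to trial termination if 2 or fewer patients demonstrate clinical benefit (CR, PR, or SD for at least 3 months"). Any lasting stable disease raises the counted rate above the response rate and lowers the chance of stopping. The documents give no stable-disease rate. For assumed clinical benefit rates, P(X ≤ 2 | 18) is about 0.71 at 10.5%, 0.27 at 20% and 0.06 at 30%. The rule is also worded as a consideration rather than a binding stop. So for the rule as written, 0.71 may well overstate the chance of stopping, and it is fair to say that 0.71 understates that chance only if the stop is based on responses.

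This does not make 0.71 correct. Section 10.2 states it for a 0.10 response rate by RECIST, beside an expected sample size and error rates that reproduce only for response counts. It does mean that changing the number without saying what it describes would be an incomplete repair.

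Finally, the practical effect may now be limited to reporting. The document is Amendment 11, and Amendment 9 had already raised accrual to 46 to reach 35 evaluable patients, which suggests, without establishing, that the first-stage decision was past.

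**Conclusion.** The stated figure is wrong. For a stop at 2 or fewer RECIST responses in 18 at a 10% response rate, the probability is 0.734 against the printed 0.71, a difference of 2.4 percentage points. The stated expected sample size of 22.5 is correct; 22.9 arises only if the wrong probability is carried forward, and is not a second error. The wrong value appears in two places, the Study Summary and section 10.2.

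The result rests on the stated boundaries, independent binomial outcomes and a first-stage count of responses. The consequence is small: no decision rule, sample size or error rate changes. Whether the interim should count clinical benefit is a separate and larger question, and the arithmetic here holds either way.

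**What to change.** Replace 0.71 with 0.73 in the Statistical Methodology entry of the Study Summary and in section 10.2. In both places, add one sentence saying that the 0.73, the 22.5 and the 0.047 assume a stop at 2 or fewer RECIST responses among the first 18 evaluable patients.

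Make the change together with any decision on the interim endpoint. If clinical benefit stays as the interim count, the added sentence should also say that the chance of stopping under that rule differs and depends on the rate of stable disease lasting at least 3 months.

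The cost is one figure and one sentence in two places. No redesign or re-analysis is needed.

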10.3 Data Analysis Plans

10.3.1 Analysis Plans for Primary Objective

The primary outcome is objective response by RECIST v1.1. The proportion of patients having an objective response by RECIST 1.1 will be estimated with a 95% exact binomial confidence interval for the efficacy population. These confidence intervals will be adjusted for the sequential nature of the two-stage procedure ²⁴.

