10.3.2 Analysis Plans for Secondary Objectives

Confidence intervals for the clinical benefit rate will be calculated similarly to RR. Progression-free survival times will be estimated using the Kaplan-Meier method. The objective response rate by irRC will be estimated similarly. Confidence intervals on the median will be constructed. Toxicities will be tabulated.

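### The primary RECIST ORR interval is adjusted for a stage 1 rule that counts clinical benefit, so it is undefined at 0–2/35 and its upper limit is too high at 3–6/35

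*Combined protocol and SAP*

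**What the plan says.** The design tests the "null hypothesis that ORR<=0.10 versus the alternative that ORR>=0.30 (where ORR is calculated via RECIST v1.1"), and 10.2 states its operating characteristics for that endpoint.

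Section 10.4.2 and the study summary set the first look at 18 evaluable patients: "consideration will be given to trial termination if 2 or fewer patients demonstrate clinical benefit (CR, PR, or SD for at least 3 months"). The final cut-off counts responders: 6 or fewer of 35 rejects the combination. The Amendment 6 entry in the amendment history confirms that clinical benefit is the intended stage 1 count.

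Section 10.3.1 specifies a 95% exact binomial interval for RECIST ORR and continues: "These confidence intervals will be adjusted for the sequential nature of the two-stage procedure". It cites a paper on confidence limits in multistage phase II trials (reference 24).

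Section 10.3.2 says "Confidence intervals for the clinical benefit rate will be calculated similarly to RR". After a sentence on Kaplan-Meier estimation of PFS it adds "The objective response rate by irRC will be estimated similarly".

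**The concern.** A two-stage exact interval is built on the set of outcomes that the stopping rule allows. With a 2/18 rule it assumes that anyone with 0, 1 or 2 events at stage 1 stops, so every stage 2 result carries at least 3 events. That is true only of the endpoint being counted at stage 1, and only if the rule is obeyed.

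Here patients with stable disease of 3 months or more can carry the trial past the gate while objective responses are 0–2 of 18, and the gate need not be followed in any case. For the primary ORR the assumed outcome set is then wrong. It omits results that can occur and gives wrong probabilities to others. At stake is the interval around the trial's main estimate when few patients respond.

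**Working it through.** **Inputs.** From 10.2 and 10.4.2: stage 1 n = 18 with threshold 2, total n = 35 with threshold 6, null 0.10, alternative 0.30. From 2.2.2: clinical benefit is CR + PR + SD of at least 3 months, so its count is never below the response count. Assumption: the documents give no CBR, so 25–50% is used. Write b(x; n, p) for the binomial probability.

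**1. The plan's own figures, counting responses at both stages.**
- Early termination: P(Bin(18, 0.10) ≤ 2) = 0.734.
- Expected N: 18 + 17 × (1 − 0.734) = 22.5.
- Rejection of the null: sum over x ≥ 3 of b(x; 18, p) × P(Bin(17, p) ≥ 7 − x). This is 0.0474 at p = 0.10 and 0.9016 at p = 0.30, so the type II error is 0.0984.

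The stated 0.047, 0.098 and 22.5 reproduce. The stated early-termination probability of 0.71 does not; the stated expected N itself implies (35 − 22.5)/17 = 0.735. That is a separate small slip.

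**2. The adjusted interval.** Stage 1 stops have probability b(x; 18, p) for x = 0, 1, 2. A stage 2 total t has probability f(t; p) = sum over x ≥ 3 of b(x; 18, p) × b(t − x; 17, p), which exists only for t ≥ 3. Each limit puts 0.025 in one tail. Two orderings were tried: stage-wise (all stage 1 stops rank lowest) and by observed rate.

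| Responses/35 | Two-stage, stage-wise | Ordinary exact | Excess in upper limit (points) |
|---|---|---|---|
| 0–2 | not defined | defined | – |
| 3 | 0.036–0.347 | 0.018–0.231 | 11.7 |
| 4 | 0.044–0.348 | 0.032–0.267 | 8.1 |
| 5 | 0.056–0.352 | 0.048–0.303 | 5.0 |
| 6 | 0.070–0.364 | 0.066–0.337 | 2.7 |
| 7 | 0.087–0.383 | 0.084–0.369 | 1.3 |
| 10 | 0.147–0.464 | 0.146–0.463 | 0.1 |

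(The last column is taken from unrounded limits.)

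The floor near 0.347 has a simple source: P(Bin(18, p) ≤ 2) falls to 0.025 only at p = 0.347. Under stage-wise ordering, no stage 2 result can therefore have an upper limit below that value. Ordering by rate changes only 3/35, because 3/35 = 0.086 lies below 2/18 = 0.111 while 4/35 = 0.114 lies above it. At 3/35 rate ordering gives 0.014–0.274.

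**3. How often ORR leaves the assumed path.** Clinical benefit of 2 or fewer implies responses of 2 or fewer, so

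P(continue with ≤ 2 responses in 18) = P(Bin(18, ORR) ≤ 2) − P(Bin(18, CBR) ≤ 2).

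At ORR 0.10:
- CBR 25%: 0.734 − 0.135 = 0.60
- CBR 35%: 0.734 − 0.024 = 0.71
- CBR 50%: 0.734 − 0.001 = 0.73

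**4. How often the trial ends at 0–2 of 35.** With q = (CBR − ORR)/(1 − ORR), sum over a = 0, 1, 2:

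b(a; 18, ORR) × P(Bin(18 − a, q) ≥ 3 − a) × P(Bin(17, ORR) ≤ 2 − a).

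| True ORR | Probability, CBR 25–50% |
|---|---|
| 10% | 0.23–0.31 |
| 15% | 0.05–0.09 |
| 20% | about 0.02 or less |

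At ORR 10% the trial ends at 3 or 4 of 35 with probability 0.38–0.42.

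**5. Coverage for ORR under the clinical-benefit gate** (rate of SD of at least 3 months varied from 0.10 to 0.40). Where it is defined, the adjusted interval covers 0.971–0.977 at ORR 0.10 and 0.975–0.989 at ORR 0.15–0.30. At ORR 0.05 it ranges from 0.961 down to 0.887. The ordinary exact interval covers 0.963–0.993 throughout.

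**The case against.** The best defence is that little turns on this. The combination is judged by a count (6 or fewer of 35), which no interval alters. At 7/35 or more, where the combination is not rejected, the two intervals nearly coincide. If the trial stops at 18 under the clinical-benefit gate, responses are also 2 or fewer, and the adjusted interval (stage-wise ordering) equals the ordinary one. Where defined, the adjusted interval errs by being too wide for ORR between 0.10 and 0.30. The ordinary upper limit also includes 0.30 at 5/35 and 6/35. The 3/35 contrast with 0.30 depends on the ordering, and reference 24 was not available to settle which ordering is meant. All of this stands, and it limits the size of the point.

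It does not remove the point. Results of 0–2/35 are likely at the null rate and the plan gives no interval for them. The 4/35 contrast holds under both orderings.

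A reader might infer that all three response intervals are invalid. The text does not support that. The adjustment is explicit only for RECIST ORR. CBR takes it by reference, and CBR is the endpoint that the current gate counts. If the gate is followed, the adjusted CBR interval is sound (coverage 0.959–0.982 for CBR 0.1–0.6). The irRC sentence follows the Kaplan-Meier sentence, so whether it inherits the adjustment is unclear. That is an ambiguity, not a stated error.

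**Conclusion.** The plan is wrong as written on this point, at moderate weight. The primary ORR interval is adjusted for a stopping rule that ORR does not trigger. It is undefined at 0–2/35 and its upper limit is 2.7 to 11.7 points too high at 3–6/35 under stage-wise ordering.

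The probabilities of leaving the assumed path rest on the assumed CBR of 25–50%. The probability of ending at 0–2/35 falls quickly as true ORR rises above 10%. The limits at 3/35 rest on the assumed ordering; those at 4/35 and above do not differ between the two orderings tried.

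It would go too far to conclude that an inactive combination could be declared active through this interval, because the 6/35 rule decides that. What the interval can do is make a low result look compatible with 30% when the data exclude it.

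**What to change.** - **10.3.1:** specify the ordinary exact (Clopper-Pearson) 95% interval at the achieved n for RECIST ORR.
- **10.3.2:** name the same method for irRC ORR.
- **Two-stage interval:** keep it only for the endpoint that triggers stage 1, which is CBR as currently written, and only if the gate is followed. State the ordering used.
- **If the gate is moved to RECIST response:** keep the adjusted interval for RECIST ORR and use the ordinary exact interval for CBR and irRC ORR. Under that gate, a stop with clinical benefit above 2/18 would have no adjusted CBR interval. The probability is 0.46–0.73 at ORR 10%, with an assumed 10–40% rate of SD of at least 3 months.

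The cost is about two sentences in 10.3, with no patients and no new data. The ordinary exact interval is slightly conservative, as the coverage figures above show.
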